6.0 Study Procedures

6.1 Research visits: STUDY1-7 (Aims 1-2)

All subjects will participate in a screening visit ([section 6.1.1](#)) then will participate in one of two substudies based on whether they are a participant recently diagnosed with T1DM (T1DM SUBSTUDY) or if they are a healthy control participant without T1DM (CONTROL SUBSTUDY). Figure 5 summaries the T1DM and CONTROL substudies.

[figure not shown]

Figure 5: Schematic for STUDY visits. Est. = estimated.

PCR=partial clinical remission. $TDD_{insulin}$ = total daily dose of insulin

1. Participants selected for the **T1DM SUBSTUDY (n=20)** will have a T1DM duration of less than one year. They will participate in three identical STUDY visits (STUDY1-3).
 - STUDY1 will occur within 1-3 months of diagnosis in most instances. In our practice, the initial starting total daily dose of insulin ($TDD_{insulin}$) upon diagnosis is usually 0.5 units/kg/day.(56) STUDY1 will require each participant's $TDD_{insulin}$ averaged over 5 consecutive days fall between 0.4-

0.6 units/kg/day, which is a common dosing range during the first 2-3 months after diagnosis.

- For participants to enter STUDY2, their mean TDD_{insulin} must be \leq 0.4 units/kg/day. This usually occurs between 3-6 months post-diagnosis.
- To enter STUDY3, the TDD_{insulin} must exceed or equal 0.6 units/kg/day, which usually occurs by 12 months post-diagnosis.

2. Participants selected for the CONTROL SUBSTUDY (n=20) will not have T1DM and have no chronic illnesses. They will participate in STUDY 4-7 (each CRC study visit follows the same protocol).

6.1.1 Initial Screening Visit

Screening visits will take place in either the Vanderbilt CRC or a room designated for research in the Eskin Diabetes Center, based on the convenience of the participant (e.g. they are already coming to a diabetes clinic visit) and availability of the room in the Eskin Diabetes Center.

The purpose of the screening visit is to obtain informed, written consent/assent, conduct a history and physical exam, instruct the participant in the use of a continuous glucose monitor and a digital insulin pen device, calculate the estimated energy requirement to be consumed before STUDY1-7 visits, and show participants how to log their food intake on their digital device.

Each screening visit will consist of the following:

6.1.1.1 Consent/Accent

The PI or designated KSP will obtain consent/assent from all participants. Consent/assent will be obtained in a private room in the CRC or Eskin Diabetes Center prior to beginning study procedures. The consent and assent form will be provided to the subject and family (if applicable) for review prior to the visit. The PI or designated Key Study Personnel will review the consent/assent forms with the family in detail and provide time for discussing any questions. The study team will provide a copy of the consent/assent form to the participant and parents if applicable.

6.1.1.2 History and Physical Exam

The PI or designee will review each subject's clinical history, perform a physical exam, and take anthropometric measurements.

6.1.1.3 Blood draw and urine collection

If the participant has not had a complete metabolic panel (CMP), complete blood count (CBC) drawn at Vanderbilt University Medical Center within six months prior to the screening visit, blood will be drawn to determine eGFR, LFTs, and hematocrit meet inclusion and exclusion criteria for study. If a CMP or CBC was drawn within six months prior to the screening, those results can be used at the discretion of the PI. HbA1c will be drawn at the screening visit.

Female participants will provide a urine sample to exclude pregnancy.

6.1.1.4 Continuous Glucose Monitor Instructions

The study team will instruct T1DM participants in the use of a continuous glucose monitor (CGM) such as Dexcom G6 or Medtronic Guardian for the monitoring of glycemia during the study. The team will then show T1DM participants how to upload both CGM data and insulin pump data (if using an insulin pump) into a HIPAA and FDA-compliant cloud-based, data-integration platform such as Dexcom Clarity, Medtronic Carelink, or Tidepool.

Although the insulin glargine dose taken by nondiabetic participants in the CONTROL SUBSTUDY before STUDY 6 and 7 is low (0.2 units/kg/day), this medication incrementally increases the risk of iatrogenic hypoglycemia. Accordingly, control participants will monitor their glucose at home during the week prior to each of the STUDY 4-7 visits. The PI may elect to use either CGMs or conventional capillary blood glucose monitors on control participants. As part of the initial screening visit, KSP will teach CONTROL SUBSTUDY to identify symptoms of hypoglycemia (e.g. shakiness, weakness, etc.), to check their glucose to confirm hypoglycemia (glucose < 70 mg/dL), and to use the commonly-taught “rule of 15” to treat a hypoglycemic episode. If a conventional capillary glucose monitor is used, KSP will instruct CONTROL SUBSTUDY participants to check their glucose each morning prior to eating and each time he or she has symptoms of hypoglycemia. If a CGM is used, the team will show the control participants how to use the CGM device. CONTROL SUBSTUDY participants using a CGM will wear the device for 7-10 days prior to each STUDY 4-7 visit.

6.1.1.5 Digital Insulin Pen Instructions for T1DM SUBSTUDY participants

The study team will provide a digital insulin pen such as the InPen (Companion Medical) or Echo (Novo Nordisk) to subjects with

T1DM who do have an insulin pump. Digital insulin pens use removable insulin cartridges and record each dose of insulin. The study team will show participants how to upload their insulin pen data using their HIPAA-compliant, FDA-approved smart phone app.

6.1.1.6 Basal insulin instructions for CONTROL SUBSTUDY participants

CONTROL SUBSTUDY participants (who do not have diabetes) will inject low doses of subcutaneous insulin glargine (0.2 u/kg/day) over 7 days preceding STUDY 6 and 7 and placebo over 7 days preceding STUDY 4 and 5. The study team will show these participants how to properly perform these injections at home. Please see section 7 regarding risk mitigation measures to prevent serious hypoglycemia.

6.1.1.7 Diet instructions

During the week preceding each STUDY visit, research participants will consume a weight-maintaining diet designed by the research team. The research team will discuss food preferences with each participant to design diet plan with standard macronutrient contents. The Mifflin-St. Jeor formula (57) will be used to calculate the estimated energy requirement (EER).

$$\text{EER for males (kcal/day)} = \text{PA} (10 \times \text{weight [kg]} + 6.25 \times \text{height [cm]} - 5 \times \text{age [y]} + 5)$$

$$\text{EER for females (kcal/day)} = \text{PA} (10 \times \text{weight (kg)} + 6.25 \times \text{height (cm)} - 5 \times \text{age (y)} - 161)$$

Where PA is the physical activity coefficient:

PA = 1.20 for little-to-no exercise

PA = 1.38 for exercising 3 times weekly

PA = 1.42 for exercising 4 times weekly

PA = 1.46 for exercising 5 times weekly

PA = 1.55 for daily exercise

PA = 1.72 for daily intense exercise or exercising twice a day every day

PA = 1.90 for daily exercise plus physical job

Where exercise is 15-30 mins of elevated heart rate and intense exercise is 45+ mins of elevated heart rate.

Macronutrient content will reflect the acceptable macronutrient distribution range of the Institute of Medicine's Recommendations for Nutrition: carbohydrate (45%–65% of energy), protein (10%–35% of energy), and fat (20%–35% of energy).(58)

The study team will use the Nutrihand and/or the MyFitnessPal software program to design meal plans and participants will log their daily caloric intake.

Nutrihand uses web-based or Smartphone app interfaces. Nutrihand creates a unique encrypted key whenever a healthcare professional adds a client to their account. That key can be used only once and by the specific email address used when the account was created. The participant will receive an automated email instructing them to log into the application for the first time. When he/she logs in, the first screen will ask the participant to agree to let the study team view their information and work with them. The participant can break the linkage with the study team at any time by removing the HIPAA key from their account.

MyFitnessPal is a smartphone app and website that tracks diet and exercise to determine optimal caloric intake and nutrients for the users' goals. Users can either scan the barcodes of various food items or manually add them in the database of over five million different foods. Users can export their nutrient and exercise log as a de-identified CSV file (an example is shown in Appendix 2). Participants will email this de-identified nutrition log to the study's email address. KSP will then upload the CSV file into the RedCAP database for subsequent data analysis.

6.1.2 Management Before and In Between STUDY 1-7 visits

Each T1DM participant's endocrinologist will manage his or her glycemic control and insulin doses before and between T1DM SUBSTUDY visits. The study team will review each T1DM SUBSTUDY study participant's insulin doses on at least a monthly basis between study visits.

Each CONTROL SUBSTUDY participant will take insulin glargine 0.2 u/kg/dose each day for seven days preceding STUDY 6 and 7 and an equal volume of a placebo injection (saline) prior to STUDY 4 and 5. The participant will be blinded to whether they are taking placebo or insulin glargine.

Although the study takes several measures to mitigate the possibility of hypoglycemia in these participants (section 7.1), the investigator will not be blinded to whether or not control participants are taking insulin prior to CONTROL SUBSTUDY participants. This enables the investigator to rapidly alter the course of the intervention in the event of hypoglycemia.

In the unlikely event severe hypoglycemia occurs (i.e. loss of consciousness or seizure due to hypoglycemia) blinding will be broken to ensure the patient's hypoglycemia is treated appropriately.

Approximately 10-14 days before STUDY visits 1-7, a study team member will contact the participant to remind them to:

1. Wear their CGM for at least the 7 days leading up to the STUDY visit for T1DM SUBSTUDY participants CONTROL SUBSTUDY participants will be reminded to wear either their study-supplied CGM or conventional capillary blood glucose monitor.
2. Record food and drink consumed for the 7 days leading up to the STUDY visit in their digital food log.

6.1.3 STUDY1-7 visits (Aims 1-2)

We will measure insulin sensitivity and endothelial dysfunction at each STUDY visit. Figure 6 summarizes the protocol of each STUDY visit. The following subsections describe the protocol in detail.

[figure not shown]

Figure 6: Schematic for STUDY visits. KVO = keep vein open

6.1.3.1 Arrival and Preparation

Preparation: To ensure an accurate measurement of key study outcomes with minimal confounding, participants will take the following precautions before each STUDY visit:

- Hold vitamin supplementation for 72 hours
- Avoid NSAIDs and aspirin for 24 and 72 hours, respectively, if feasible

- Refrain from smoking and avoid secondhand smoke exposure for 12 hours
- Consume no caffeine for 12 hours
- Abstain from exercise for 12 hours

Study participants will arrive to the CRC between 1700-2100 on the evening prior to STUDY visits.

[figure not shown]
CRC staff will draw the following labs prior to conducting the clamp study:

- Pregnancy test (urine or blood) on female participants to rule out pregnancy.
- I-STAT potassium: to screen for hypokalemia

T1DM participants who use an insulin pump will discontinue and detach their insulin pump at 2130 on the night of CRC admission. T1DM participants who take multiple daily insulin injections take their last basal insulin analog dose on the evening prior CRC admission and hold their basal insulin dose on the evening of admission. CRC staff or KSP will place an intravenous angiocatheters in each arm.

6.1.3.2 Overnight insulin infusion (T1DM SUBSTUDY participants only)

At 2200 a continuous, IV infusion of regular human insulin (recombinant DNA origin) will be given to T1DM participants according to the protocol of Goldberg et al.(59), modified for use in healthy patients with T1DM (Appendix 1). This protocol targets a glucose of 90-120 mg/dL by the next morning. CRC staff will check blood glucose of T1DM participants on an hourly basis using a calibrated, hospital bedside glucose monitor. This protocol was implemented in a previous study (IRB # 161504) and achieved ideal glycemic control as shown in the figure below (n=9 T1DM participants, figure shows means \pm SD for glucose and means for insulin infusion rate).

Should glucose fall to < 75 mg/dL, the PI may elect to infuse a small dose of 20% dextrose to prevent hypoglycemia. Should glucose fall to < 55 mg/dL and the patient experiences symptoms of hypoglycemia, 20% dextrose will be at bedside to treat the hypoglycemia (e.g. 75 mL of 20% dextrose delivers 15 gm of glucose). If glucose were to fall to < 55 mg/dL, the PI will postpone the following morning's clamp study to a later date because of the confounding influence of the counter-regulatory response to hypoglycemia.

The PI will be readily available to CRC nursing staff via telephone and [REDACTED]

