6.1.3.13 Rescheduling STUDY visit after a technical issue

It is possible once a clamp visit has begun a technical issue will prevent the successful completion of the study. For example, IV access may be lost during the study or otherwise uneventful hypoglycemia (glucose < 55 mg/dL) may occur for those participants receiving an overnight IV insulin infusion. In the event such a technical issue occurs, the PI may elect to reschedule a new, repeat STUDY visit provided he deems the technical issue poses no serious danger to the participant were it to occur again and the participant wishes to repeat the study.

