- Bolus 100 mL of D20 (20 gm of glucose) immediately
- Contact PI ([name], mobile: [REDACTED] pager [REDACTED])
- Check BG q 15 minutes
- When BG is ≥ 90 mg/dL, wait 1 hour, recheck BG. If still ≥ 90 mg/dL, restart insulin infusion at 50% of the most recent rate

IF BG 55-69 mg/dL:

STOP INSULIN INFUSION

- Contact PI immediately ([name], mobile: [REDACTED] pager [REDACTED])
- Prepare to give D20 at approximately 3.0 mg/kg/min after discussing with PI.
- Check BG q 15 minutes
- When BG is ≥ 90 mg/dL, wait 1 hour, recheck BG. If still ≥ 90 mg/dL, restart insulin infusion at 75% of the most recent rate

IF BG > 70 mg/dL:

STEP 1: Determine the CURRENT BG LEVEL. This identifies a COLUMN in the table:

BG 70-89 mg/dL	BG 90-119 mg/dL	BG 120-179 mg/dL	BG \geq 180 mg/dL
----------------	-----------------	------------------	---------------------

STEP 2: Determine the RATE OF CHANGE from the prior BG level. This identifies a CELL in the table. Then move to the right for **INSTRUCTIONS**. (Note: if the last BG was measured less than an hour before the current BG, calculate the hourly rate of change. Example: if the BG at 0200 was 85 mg/dL and an additional BG is checked early at 0230 was 70 mg/dL, the total change over 30 minutes is -15 mg/dL; however, the hourly rate of change is $-15 \text{ mg/dL} \times 2 = -30 \text{ mg/dL}$).

BG 70-89 mg/dL	BG 90-119 mg/dL	BG 120-179 mg/dL	BG \geq 180 mg/dL	INSTRUCTIONS*
		BG \uparrow by > 40 mg/dL/hr	BG \uparrow	\uparrow INFUSION by “ 2Δ ”
	BG \uparrow by > 20 mg/dL/hr	BG \uparrow by 1-40 mg/dL/hr OR BG UNCHANGED	BG UNCHANGED OR BG \downarrow by 1-40 mg/dL/hr	\uparrow INFUSION by “ Δ ”
BG \uparrow	BG \uparrow by 1-20 mg/dL/hr, BG UNCHANGED, OR BG \downarrow by 1-20 mg/dL/hr	BG \downarrow by 1-40 mg/dL/hr	BG \downarrow by 41-80 mg/dL/hr	NO INFUSION CHANGE
BG unchanged OR BG \downarrow by 1-20 mg/dL/hr	BG \downarrow by 21-40 mg/dL/hr	BG \downarrow by 41-80 mg/dL/hr	BG \downarrow by 81-120 mg/dL/hr	\downarrow INFUSION by “ Δ ”
BG \downarrow by > 20 mg/dL/hr see below†	BG \downarrow by > 40 mg/dL/hr	BG \downarrow by > 80 mg/dL/hr	BG \downarrow by > 120 mg/dL/hr	HOLD x 30 min, then \downarrow INFUSION by “ 2Δ ”

Protocol Version #:6

Protocol Date: July 29, 2021

53

***CHANGES IN INSULIN INFUSION RATE** (“ Δ ”) are determined by the current rate:

Current Rate (units/hr)	Δ = Rate Change (units/hr)	2Δ = 2X Rate Change (units/hr)
≤ 1	0.25	0.5
>1-3	0.5	1
> 3	1	2

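### For an overnight glucose below 55 mg/dL, the protocol's sections disagree on what triggers dextrose and on whether the clamp visit must be repeated

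*Combined protocol and SAP*

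**What the plan says.** - **Section 6.1.3.2** (T1DM substudy only) runs the overnight insulin infusion under Appendix 1. Below 75 mg/dL the PI has the option of a small amount of 20% dextrose. For a deeper fall it says: "Should glucose fall to < 55 mg/dL and the patient experiences symptoms of hypoglycemia, 20% dextrose will be at bedside to treat the hypoglycemia", with the example that "75 mL of 20% dextrose delivers 15 gm of glucose". On the clamp it says: "If glucose were to fall to < 55 mg/dL, the PI will postpone the following morning's clamp study to a later date", and gives the reason: "because of the confounding influence of the counter-regulatory response to hypoglycemia".
- **Section 7.1.2** repeats the 75 mL (15 g) figure, again as an example and without mentioning symptoms.
- **Appendix 1**, at any reading below 55 mg/dL, stops insulin and orders: "Bolus 100 mL of D20 (20 gm of glucose) immediately". Staff also call the PI and check glucose every 15 minutes. Once glucose has reached 90 mg/dL and is still there an hour later, they "restart insulin infusion at 50% of the most recent rate". The appendix describes the infusion as running on through the morning clamp and is silent on postponement.
- **Section 6.1.3.13** lists a glucose below 55 mg/dL during overnight IV insulin as an example of a technical issue, after which "the PI may elect to reschedule a new, repeat STUDY visit". The conditions are that the PI sees no serious danger in a recurrence and that the participant is willing.
- **Section 6.1.3.4** covers controls on overnight IV insulin (STUDY 5 and 7). It starts IV glucose below 75 mg/dL. It has no separate instruction below 55 mg/dL and no postponement rule.

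**The concern.** Two things are at stake.

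The first is care at the bedside. A participant who reads below 55 mg/dL overnight without symptoms gets a fixed response under Appendix 1. Under section 6.1.3.2 only the optional provision for readings below 75 mg/dL clearly reaches that participant. T1DM participants may be as young as 15.

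The second is consistent handling of visits. The protocol itself says that such a reading confounds the next clamp, and for that reason makes postponement mandatory in one section. Another section makes a repeat visit optional after the same event. Two participants with the same reading could therefore end with a repeat clamp in one case and a missing visit in the other, depending on which section was followed. Controls given overnight IV insulin are exposed to the same confounding, but no mandatory rule reaches them.

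**Working it through.** **1. Dextrose amounts.** A 20% solution holds 0.20 g/mL.

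- Section 6.1.3.2 and section 7.1.2: 75 × 0.20 = 15 g, as stated.
- Appendix 1: 100 × 0.20 = 20 g, as stated.
- Difference: 20 − 15 = 5 g; ratio: 100/75 = 1.33.

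Both conversions are right, so there is no arithmetic slip. What differs is the texts.

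**2. The provisions side by side, for glucose below 55 mg/dL.**

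| Place | Trigger for dextrose | Amount | Next clamp |
|---|---|---|---|
| 6.1.3.2 (T1DM) | reading plus symptoms | 15 g, example | postponement mandatory |
| 7.1.2 | hypoglycemia; symptoms not mentioned | 15 g, example | not addressed |
| Appendix 1 (T1DM) | reading alone | 20 g, ordered | not addressed; insulin restarted after recovery |
| 6.1.3.13 (any overnight IV insulin) | not addressed | not addressed | repeat visit at PI's discretion |
| 6.1.3.4 (STUDY 5 and 7) | IV glucose below 75 mg/dL; nothing specific below 55 | not stated | not addressed |

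**3. Treatment.** The trigger is the firmer conflict, because one text attaches symptoms to the reading and the other does not. The amounts are a weaker conflict, since 15 g is an illustration and 20 g is an order.

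**4. Clamp.** Section 6.1.3.2 moves the clamp to a later date, which implies a further visit. Section 6.1.3.13 starts from a visit that could not be completed and makes the further visit optional. They disagree on whether the visit has to be repeated. They do not disagree on whether a clamp may be run that morning: only section 6.1.3.2 speaks to that, and it says no.

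**5. Reach.** Section 6.1.3.2 is limited by its title to T1DM participants. Section 6.1.3.13 applies to anyone on overnight IV insulin, so it is the only rule covering STUDY 5 and 7.

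**6. What a lost visit costs.** Table 7 plans n = 20 in each substudy. A lost visit that belongs to the power contrast removes one pair: 1/20 = 5%. Section 10.1.3 enrols 23 per substudy, a margin of 23 − 20 = 3, which is already meant to cover a 15% drop-out. The documents do not say how often glucose falls below 55 mg/dL, so the expected number of lost visits cannot be computed.

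**The case against.** The strongest reply is that much of this is loose drafting with no real conflict. Section 6.1.3.2 says only that dextrose is at hand; it does not forbid treating a participant without symptoms, and it names Appendix 1 as the governing protocol. The 75 mL figure is an example in both places where it occurs. Appendix 1 has staff call the PI, who is the person responsible for postponing. Restarting insulin is not an order to run a clamp, because a participant whose home pump is disconnected still needs insulin. Section 6.1.3.2 also reports that the protocol controlled glucose well in nine earlier T1DM participants, and Appendix 1 already stops insulin at 55–69 mg/dL, so readings below 55 may be rare.

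Most of this stands, and it limits the point. The gap in Appendix 1 is an omission; it does not contradict postponement. The 5 g difference sets an example against an order. Two things survive: the symptom condition appears in one text and is absent from the text it cites, and a mandatory rule in section 6.1.3.2 meets a discretionary one in section 6.1.3.13 for the same event. Rarity lowers the number of visits affected but does not tell staff which text to follow.

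A reader might go further and infer that the PI can choose which post-hypoglycemia glucose infusion rates enter the analysis. The documents do not support that. Section 6.1.3.13 presumes an uncompleted study, so its choice is between a repeat visit and a missing one. Nor does the unblinded investigator in section 6.1.2 support it for the T1DM substudy: that statement concerns insulin glargine and placebo in the control substudy, whereas STUDY 1–3 are not randomised and have no planned blind.

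**Conclusion.** The inconsistency is real and should be corrected. In the T1DM substudy, section 6.1.3.2 and Appendix 1 differ on the trigger for dextrose below 55 mg/dL, and sections 6.1.3.2 and 6.1.3.13 differ on whether the visit must be repeated. For STUDY 5 and 7 only the discretionary rule applies, although the protocol's own reason for postponing holds equally there.

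The size is modest: 5 g between an example and an order, and up to one of 20 planned pairs for each visit that is not repeated. No effect on the primary glucose infusion rate contrast is claimed. It would be tempting to compute one by assuming that a confounded clamp is kept and shifts that participant's difference. No section authorises keeping such a clamp, and the documents give no size for the shift. The conclusion rests on reading the texts together and needs no assumption about event frequency.

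**What to change.** The investigator and the safety monitor should reconcile sections 6.1.3.2, 6.1.3.13 and 7.1.2 with Appendix 1, so that all of them carry:

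- one instruction on treating a reading below 55 mg/dL, covering the trigger and the amount;
- one instruction on whether the clamp is postponed and whether the visit is repeated.

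The postponement decision should also be written into Appendix 1, since that is the order set used overnight. The protocol should state whether it applies to controls in STUDY 5 and 7. The clinical content is for the investigator and safety monitor to decide; nothing here favours one version.

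The cost is a wording amendment. If repetition is made mandatory, a few visits may have to be repeated, which section 6.1.3.2 already foresees for T1DM participants.
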